# F & G. Methodology - Intervention, Study Procedures and Data Collection

#### **The Intervention**

Conceptual Model. We will use Social Cognitive Theory (SCT) and Self-Determination Theory (SDT) to guide program development and selection of measures. SCT stipulates that behavior modification results from the interaction between behavior change, cognition (self-efficacy, perception of barriers to lifestyle changes), and the environment (support), while modeling and reinforcement serve to encourage change. SDT is a broad-based theory of human motivation that explains how intrinsic motivation can lead to improve eating and exercise patterns. According to SDT, a person's increased intrinsic motivation to improve eating and exercise patterns should positively relate to self-efficacy and the ability to overcome barriers and solicit support. The DPP plus breastfeeding (Tx1) uses assignments, individualized goal setting, and shared problem-solving to increase mastery and goal achievement in incremental steps to enhance self-regulatory skills.

**Diabetes Prevention Program (DPP).** [name] and the research coordinator will administer the DPP in two phases. Phase I consists of a total of 16 sessions that will be completed during pregnancy (see Table 2). Two of the Phase I DPP sessions have been replaced with the Cooking Matters curriculum: DPP session #2 has been replaced with creating a healthy home food environment, and DPP session #4 with incorporating more fruits, vegetables,

and whole grains into family meals. Cooking Matters empowers low-income families with the skills to cook healthy, affordable meals at home. Its curriculum uses the Dietary Guidelines for Americans and MyPlate as the foundation for basic nutrition guidelines. Each of the sixteen (16) sessions/modules of Phase I will be pre-recorded and archived on a secure, private group on Facebook. Only Tx1 and Tx2 participants, [name] and the research coordinator will have access to this Facebook group.

We will employ a "rolling" recruitment period of 9 months, meaning that each participant may be at different completion stages. During their first face-to-face orientation session, participants will receive access to the secure, private group on Facebook. They will be asked to complete each Phase I module on their own time, starting at week 19 of pregnancy. To supplement their self-study of the curriculum, on a weekly basis, the research coordinator will follow up with each study participant via phone to check on progress. If participants do not make adequate progress, then the coordinator will assess how much extra time the participant needs to complete a module, and will work with her face-to-face via Skype, FaceTime or Zoom if needed. Participants will complete Phase I by week 33 of pregnancy.

Phase II consists of a total of 15 sessions that will be completed after delivery (see Table 2). Two of the Phase II DPP sessions (sessions #4 and #5 respectively) have been modified with the Cooking Matters curriculum that (1) emphasizes planning/preparing for healthy, low-cost meals and (2) encourages mothers to make smart choices when food shopping. Each of the fifteen (15) sessions/modules of Phase II will be pre-recorded and archived on the same secure, private group on Facebook mentioned above. Only Tx1 and Tx2 participants, [name] and the research coordinator will have access to this Facebook group.

Participants will re-engage into the DPP with another face-to-face orientation session conducted by [name] at week 6 postpartum. The same session completion format and procedure for inadequate progress will be followed as during pregnancy. Participants will complete Phase II by week 20 postpartum. An 80% completion rate of each phase is considered successful completion of the intervention.

Table 2. Timetable - Diabetes Prevention Program Sessions

Prenatal (Core Curriculum)	Postnatal (Post-core Curriculum)				
	Week of		Week of		
DPP Sessions - Phase I	Pregnancy	DPP Sessions - Phase II	Postpartum		
1 - Orientation - Welcome!	18	1 - Orientation - Welcome Back!	6		
2 - Cooking Matters (CM): Set a Healthy Example	19	2 - Fats: Saturated, Unsaturated, & Trans-Fats	7		
3 - Eating Less Fat and Fewer Calories	20	3 - Food Preparation & Recipe Modification	8		
4 - CM: Choosing Fruits, Vege's, Whole Grains	21	4 - Taking It One Meal at a Time, CM: Planning	9		
5 - Move Those Muscles	22	5 - Variety and Balance, CM: Shopping	10		
6 - Being Active - A Way of Life	23	6 - More Volume, Fewer Calories	11		
7 - Tip the Calorie Balance	24	7 - Staying on Top of Physical Activity	12		
8 - Take Charge of What's Around You	25	8 - Stepping Up to Physical Activity	13		
9 - Problem Solving	26	9 - Long-term Maintenance	14		
10 - Four Keys to Healthy Eating Out	27	10 - Holidays, Vacations, Special Events	15		
11 - Talk Back to Negative Thoughts	28	11 - Preventing Relapse	16		
12 - The Slippery Slope of Lifestyle Change	29	12 - Stress and Time Management	17		
13 - Jump Start Your Activity Plan	30	13 - Heart Health	18		
14 - Make Social Cues Work for You	31	14 - A Closer Look at Type 2 Diabetes	19		
15 - You Can Manage Stress	32	15 - Looking Back and Looking Forward	20		
16 - Ways to Stay Motivated	33				

**Breastfeeding.** Additionally, participants in Tx1 will receive an educational session on breastfeeding and will register for and participate in a professional peer support group (see Table 3). Participants in Tx2 and Tx3 will not receive breastfeeding education or register/participate in a professional peer support group. The 2-hour breastfeeding session is pre-recorded into four (4) 30-minute sessions and archived on the same secure, private Facebook group as mentioned previously. Participants will have access to all four breastfeeding sessions by week 24 of pregnancy and they need to complete all sessions by week 30 of pregnancy. The breastfeeding session will be taught by an International Board Certified Lactation Consultant (IBCLC).

At delivery, all participants will receive some type of lactation support in the hospital. However, only participants in Tx1 will be provided with a breastfeeding assessment at day 3, day 10, week 3 and week 6, as well as months 2, 3 and 6 postpartum (see Table 3). The breastfeeding telephone assessment is modelled after the Bristol Breastfeeding Assessment Tool (BBAT) (see Appendix 6) and used to improve an infant's positioning, attachment, sucking, and swallowing. During these telephone assessments, [name] research coordinator will assess if mother and baby need breastfeeding support from a lactation professional. If the telephone assessment warrants an in-person visit, then the research coordinator will put mother and baby in contact with a lactation professional provided by the hospital.

Table 3. Breastfeeding Support for Women in Tx1 (Intervention Arm) Only

	Prenatal	Postnatal								
Intervention Components	Week 24 - 30	Day 3	Day 10	3 Weeks	6 Weeks	2 Months	3 Months	6 Months		
Breastfeeding Education (2-hour curriculum)	X									
Breastfeeding Professional Peer Support	Participants initiate contact		Particip	oants atter	nd 2 to 4 s	essions as	needed			
Breastfeeding Telephone Assessment (15-20 minutes)		Х	Х	Χ	Х	Χ	Χ	Χ		

**Breastfeeding curriculum.** The Kansas Breastfeeding Coalition, Inc. (KBC) in partnership with the Kansas Department of Health and Environment (KDHE) Bureau of Family Health (Title V

Maternal and Child Health Services Program) created a 2-hour breastfeeding class for parents and parents-to-be. The curriculum aligns with nutritional requirements set by the U.S. Department of Agriculture's Special Supplemental Nutrition Program for Women, Infants, and Children (WIC) and with parenting and maternity care practices of specific Kansas-based organizations such as the Kansas Infant Death and SIDS Network, Inc. 111 and the United Methodist Health Ministry Fund's High 5 for Mom & Baby. 112 Further, the curriculum is based on the Office on Women's Health "Your Guide to Breastfeeding." 113 The content of the 2-hour session will focus on the following areas: establishing and maintain a sufficient and safe breast milk supply, breast anatomy and physiology, maternal diet and lifestyle choices, prescription and non-prescription medications, infant stomach capacity, baby behavior feeding cues, breast milk expression, safe handling and storage of breast milk, returning to work, safe preparation of infant formula, biologically appropriate bottle feeding, and local community breastfeeding resources.

Potential survey participants will have the option of contacting researchers with any questions prior to completing the survey or prior to participating in the educational session, and will self-administer the survey if wanting to participate. Responses will be entered in REDCap for data analysis. All identifying information will be removed from the data prior to analysis. Research personnel will not have access to any identifying information contained in the survey.

Self-Administered Surveys and Incentive to Participate. All surveys will be self-administered (Appendix 1 through 5 – Survey Instruments) and are available in English. The pre- and post-survey instruments are identical. They will be administered electronically at baseline (at study entry) and at six months postpartum (see Table 5 Data Collection). Via email, the study coordinator will provide each participant with a REDCap link that provides electronic access to each survey. Informed consent will occur when the participant opens the survey. Participants will self-administer the survey and may stop at any time. Potential survey participants will have the option of contacting researchers with any questions prior to completing the survey. The survey instrument will be set up using REDCap and responses will be automatically entered and stored in REDCap for data analysis. All identifying information will be removed from the data prior to analysis. Research personnel will not have access to any identifying information contained in the survey.

At recruitment and at study closure 6 months postpartum, all participants will complete four preand post-survey instruments: (1) Breastfeeding assessment, socio-demographic characteristics, and health status (sociodemographic and health status questions will only be asked at baseline, not at study closure) (Appendix 1); (2) Breastfeeding Self-Efficacy Scale-Short Form (BSES-SF) (Appendix 1); (3) Kaiser Physical Activity Survey (KPAS) (Appendix 2); (4) the Eating At America's Table Study (EATS) Fruit & Vegetable Intake Screener (Appendix 3) supplemented with questions on fiber, added sugars, dairy, calcium, and meat from the Dietary Screener in the National Health and Nutrition Examination Survey (NHANES 2009-10) (Appendix 4). (Appen

evidence shows that higher BMI pregnant women may have an increased likelihood of postnatal depression. Therefore, at 6 weeks postpartum, all participants will complete the Edinburgh Postnatal Depression Scale (EPDS) (Appendix 5), 127-129 which takes about 5 minutes. Participants with an EPDS score of 10 or higher will be referred to a mental healthcare professional for further psychological evaluation. All study survey instruments are listed in Table 4.

Table 4. Survey Instruments

Study Instrument	Items Measured	No. of Items	Reliability	Populations Validated		
Breastfeeding Knowledge Assessment, Socio- demographic Characteristics, and Health Status	To assess knowledge of breastfeeding (44 items), to assess socio-demographic characteristics (6 items), to assess health status (7 items)	57 items: multiple choice	Not yet performed.	Not yet performed.		
Breastfeeding Self-Efficacy Scale-Short Form (BSES-SF)	To assess levels of self- efficacy in postpartum women. BSES-SF has also been used with prenatal women.	scale.	Crohnbach's alpha = 0.97	Postpartum women at 1 week, 4 weeks, and 8 weeks.		
Kaiser Physical Activity Survey (KPAS)	To assess multiple domains of physical activity and total physical activity in pregnant women.	activities, occupational	Correlation coefficient for total activity: $r = 0.84$ ; correlation coefficient for multiple domains: $r = 0.76 - 0.86$	Pregnant women aged 18 to 47 years old.		
Fruit & Vegetable Intake Screener (EATS)	To assess intake of fruits and vegetables.	10 items; with portion-size questions.	Correlation coefficient between test instrument and true intake: $r = 0.51-0.67$ Correlation coefficient between three screeners: $r = 0.52 - 0.71$	Men and women aged 20 to 70 years old.		
Selected items from the Dietary Screener Questionnaire (NHANES 2009-10)	To assess intake of fiber, added sugars, dairy, calcium, and meat.	Up to 6 selected items on fiber, added sugars, dairy, calcium and meat; DSQ has a total of 26 items.	Not yet performed.	Not yet performed.		
Edinburgh Postnatal Depression Scale (EPDS)	To assess levels of depression during the postpartum period.	10 items	Sensitivity: 34-100% Specificity: 44-100% Positive likelihood ratios: 1.61-78	Antepartum and postpartum women.		

Each participant will receive a \$50 gift card at consent, after she will deliver her baby, the participant will receive a digital scale and a pedometer, and upon completion of the study (at 6 months after birth), each participant may select a gift up to \$75 for their baby from their baby registry at Walmart. In summary, for participants randomized to any of the three groups: 1) DPP plus breastfeeding, or 2) DPP only, or 3) Usual care, the total possible compensation is valued at \$187.50 including the following gift items: digital scale (valued at \$50 each), pedometer (valued at \$12.50 each), baby gift at Walmart (valued at \$75 each), and a \$50 gift card.

If a participant ends early prior to completing the study, then she will only receive the items for the program components that she completed.

Study payments are taxable income. Prior to distribution of gift items and after obtaining consent, a form 1099 will be provided to each participant for completion. This process is in accordance and in compliance with regulations set forth by the University of Kansas School of Medicine and the Internal Revenue Service if you receive \$600 or more in a calendar year for participating in research studies.

Aim 3: Test the efficacy of Tx1 to increase any breastfeeding through 6 months postpartum among women with a BMI  $\geq$  25. Hypothesis 3: Women in Tx1 will breastfeed longer compared to women in Tx2 and Tx3. At delivery, breastfeeding initiation will be measured (see Table 5). This is defined as starting breastfeeding immediately after delivery. We

will also measure the duration of any breastfeeding (defined as predominant breast milk with some formula supplementation) as outlined in Table 5 below. Further, we will measure exclusivity of breastfeeding (defined as exclusive breast milk without supplementation unless medically necessary), formula supplementation, and solid foods. We will measure formula and solid food at the time that they were first introduced as well as quantity and frequency of feedings.

Table 5. Timeline: Data Collection for All Study Participants

	Prenatal			Postnatal							
Measurements	Baseline	Week 24	Week 28	Week 32	Week 36	Delivery	1 Week	3 Weeks	6 Weeks	3 Months	6 Months
Breastfeeding Knowledge, demographics, health status	Χ										Χ
Breastfeeding Self-Efficacy Scale-Short Form (BSES-SF)	Х										Χ
Kaiser Physical Activity Survey (KPAS)	X										Χ
Fruit & Vegetable Intake Screener (EATS)	X										Χ
Selected items from DSQ (NHANES 2009-10)	Х										Χ
Mother's Weight (lbs)	Х					Х	Χ	Χ	Χ	Χ	Χ
Mother's Height (inches)	Х										
Glucose tolerance	Х										
Mother's HbA1c	Х										Χ
Mother's Mean Arterial Blood Pressure	Х					Χ					Χ
Baby's Weight (kg)						Х	Х	Х	Х	Х	Χ
Baby's Height (gm)						Х	Х	Х	Х	Х	Χ
Breastfeeding Initiation at Delivery						Χ					
Breastfeeding Duration (any and exclusive)							Χ	Х	Х	Х	Χ
Formula Supplementation						Х	Χ	Χ	Χ	Χ	Χ
Solid Foods							Х	Х	Х	Х	Χ

Sample Size and Randomization. The primary outcomes of interest are: (1) postpartum weight loss; (2) HbA1c and mean arterial blood pressure; and (3) breastfeeding duration. A total of 60 participants (20 per study arm) will be recruited. The results from this pilot study will be used in sample size estimation for a future study that is sufficiently powered to detect a clinically meaningful effect size. Due to the nature of this project being a feasibility study, the sample size in the proposed study is not based on providing adequate power to detect a clinically meaningful effect size across the three study arms. Block randomization with block size of 5 participants will be employed. A sequence of 12 random integers will be generated using a computer algorithm. The first 4 integers of the sequence will be assigned to the DPP plus breastfeeding arm; the next 4 integers will be assigned to the DPP only arm; and the last 4 will be assigned to the usual care arm. Blocks will be assigned to arms in the increasing order of sequence of integers generated.

**Statistical Analysis.** For baseline data characteristics, descriptive statistics will be reported as mean and standard deviation for continuous variables and as count and percentage for categorical variables. Depending on the distribution of the continuous variables, the Kruskal-Wallis test or ANOVA will be used to test for differences in continuous variables across the three arms. Chi-

Square test of independence (or Fishers exact test if 25% of cells have counts less than 5) will be used to assess the association between categorical variables and the three arms. The analysis will be based on "intention-to-treat" principle. A two-sided alpha level of 0.05 will be used to determine statistical significance. A 95% confidence interval will also be reported.

Aim 1: Test the efficacy of Tx1 to improve 6-month postpartum weight loss among women with a BMI  $\geq$  25. The outcome of interest is 6 month postpartum weight loss measured across the three arms. Weight will be measured at delivery, and at weeks 1, 3, and 6 postpartum and at 3 months (13 weeks) and 6 months (26 weeks) postpartum. The difference in postpartum weight (weight loss) between two consecutive time points will be computed. Thus, each participant has 5 postpartum weight loss values based on weight measurements at 6 different time points. We will use the generalized estimating equation approach to compare weight loss in the DPP plus breastfeeding arm (Tx1) with weight loss in the DPP only (Tx2) and usual care (Tx3) arms, as well as weight loss between Tx2 and Tx3. The working correlation matrix will be specified after assessing the data. The model will be adjusted for the effect of age, race/ethnicity, level of education, annual household income, family history of diabetes, baseline weight, pre-diabetes status, and parity.

Aim 2: Test the efficacy of Tx1 to improve 6-month postpartum mean blood glucose (HbA1c) and mean arterial blood pressure among women with a BMI  $\geq$  25. The outcome of interest is mean blood glucose (HbA1c) and mean arterial blood pressure ((systolic blood pressure +2 (diastolic blood pressure)/3)) measured at baseline, delivery, and at 6 months postpartum across the three arms. We will use a multiple linear regression approach to compare HbA1c in Tx1 with HbA1c in Tx2 and Tx3, as well as HbA1c between Tx2 and Tx3. The model will be adjusted for the effect of age, race/ethnicity, level of education, annual household income, family history of diabetes, pre-diabetes status, parity, and baseline weight. The difference in mean blood arterial pressure at 6 months postpartum will also be assessed using a separate multiple linear regression approach after adjusting for the same covariates listed previously.

Aim 3: Test the efficacy of Tx1 to increase any breastfeeding through 6 months postpartum among women with a BMI  $\geq$  25. The outcome of interest is breastfeeding through 6 months postpartum; it will be measured at delivery, and at weeks 1, 3, and 6 postpartum and at 3 months (13 weeks) and 6 months (26 weeks) postpartum. The risk of stopping "6 month postpartum breastfeeding" in Tx1 relative to Tx2 and Tx3 will be estimated using Zou's modified Poisson regression approach. The outcome in Zou's modified Poisson regression is binary, and it does not take into account the time until which any breastfeeding was done before stopping. However, it provides an interpretation-friendly estimate of the probability of stopping "6 month postpartum breastfeeding." Additionally, the Cox Ph model will be used to compare the risk (hazard) of stopping breastfeeding across each study arm. Unlike Zou's modified Poisson approach, the Cox model takes into account the time of breastfeeding. Any participants who are lost to follow-up will be treated as censored events and participants who stop

breastfeeding during the follow-up are the events of interest. In addition, participants who performed any breastfeeding until 6 months will be treated as administratively censored events. The model will be adjusted for the same covariates listed above under Aims #1 and #2.

Missing data. Owing to the design of the study and non-transient nature of the study population, we anticipate few to none missing observations. Any missing observation that can be attributed to either attrition or nonresponse will be considered missing at random. Depending on the proportion of missingness, complete case analysis (less than 5% missing) or the multiple imputation method will be used to impute missing data. For longitudinal response (postpartum weight measurements), the last observation will be carried forward to impute the missing response. Results based on imputed data will be compared to findings from complete case analysis, to assess the effect of missingness on study findings.

Comparison of scores on the Breastfeeding Assessment, BSES-SF, KPAS, EATS, and selected items from the DSQ. The Breastfeeding Assessment is based on 44 questions. Cronbach's alpha will be used to test the internal consistency of the data. The "difference in Breastfeeding Assessment scores between recruitment and at study closure" across all three study arms will be assessed using the multiple linear regression approach. The model will be adjusted for the effect of age, race/ethnicity, level of education, annual household income, family history of diabetes, pre-diabetes status, and parity. The BSES-SF score is based on 14 questions and ranges from 14 to 70 points. Cronbach's alpha will be used to test the internal consistency of the data. The "difference in BSES scores between recruitment and at study closure" across all three study arms will be assessed using the multiple linear regression approach. The model will be adjusted for the effect of age, race/ethnicity, level of education, annual household income, family history of diabetes, pre-diabetes status, and parity. The KPAS score comprises of 38 questions that are distributed sequentially but non-uniformly across four sections and measure household and family care activities (household index); occupational activities (occupational index); active living habits (active living index); and participation in sports and exercise (sports and exercise index). For each section, Cronbach's alpha will be used to test the internal consistency of the data. For each index of physical activity, "difference/change between recruitment and at study closure" across all three study arms will be assessed using the multiple linear regression approach after adjusting for the effect of the previously stated covariates. The EATS survey consists of 10 questions, and up to 6 questions will be selected from the DSQ. For each question, counts and percentages will be reported for participants at recruitment and at study closure across all three study arms.

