diet, exercise, and behavior modification. There is also evidence to support the use of this efficacious program in reducing postpartum weight. Further, recent evidence suggests that longer duration of breastfeeding is associated with lowering T2DM incidence, reducing maternal postpartum weight, and resetting maternal metabolism after pregnancy. Breastfeeding also protects against breast cancer, ovarian cancer, and T2DM. Despite these findings, no studies have addressed the role of intensive breastfeeding support combined with an efficacious weight loss program to reduce postpartum weight, thereby reducing progression to T2DM after pregnancy.

The American Academy of Pediatrics and the World Health Organization recommend breastfeeding for the first 6 months of life. In Kansas,  $79\%^{73}$  of women with a BMI  $\geq 25$  start breastfeeding, and only  $29\%^{73}$  still breastfeed with some supplementation (defined as "any breastfeeding") at 6 months postpartum. The Kansas rate for high BMI women of 29% is unacceptable and an urgent public health concern when compared to the 6-month breastfeeding rate for normal BMI Kansas women of 51% and the Healthy People 2020 goal of 61%. In the proposed randomized controlled trial, we seek to determine the feasibility and efficacy of a combined breastfeeding, DPP-based program in a cohort of overweight/obese women to be followed during pregnancy through 6 months postpartum. Our trial will have three study arms: DPP plus breastfeeding (Tx1); DPP Only (Tx2); and Usual Care (Tx3). A total sample of 60 pregnant women in their 1st or 2nd trimester with a BMI  $\geq 25$  will be recruited. Eligible participants are randomly assigned to a study arm (20 per arm).

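### The Aim 3 definition of 'any breastfeeding' leaves out some women who are still breastfeeding, and it conflicts with the plan's own event wording

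*Combined protocol and SAP*

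**What the plan says.** Four places in the combined protocol and SAP bear on this outcome.

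- **Section III, Outcome Measures, Aim 3.** Any breastfeeding is "defined as predominant breast milk with some formula supplementation". Exclusivity follows as a further measure, "defined as exclusive breast milk without supplementation unless medically necessary". Table 5 collects both in one duration row at weeks 1, 3 and 6 and months 3 and 6.
- **Section III, Sample Size and Randomization.** The third primary outcome is labelled "and (3) breastfeeding duration". The Aim 3 objective is "to increase any breastfeeding through 6 months postpartum".
- **Section III, Statistical Analysis, Aim 3.** For the Cox model, women who stop "breastfeeding during the follow-up are the events of interest", and "participants who performed any breastfeeding until 6 months will be treated as administratively censored events". The modified Poisson model takes stopping by 6 months as a binary outcome.
- **Section I.B, Background and Significance.** The 29% Kansas figure for women with BMI of 25 or more counts those who "still breastfeed with some supplementation (defined as 'any breastfeeding') at 6 months postpartum". The word 'predominant' does not appear there.

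Nowhere does the plan say that 'any' includes exclusive feeding, how a mostly-formula mother who still breastfeeds is classified, or what share of feeds makes breast milk predominant.

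**The concern.** In ordinary use, any breastfeeding is the widest category and exclusive breastfeeding lies inside it. Here 'any' is written as a middle category: breast milk must predominate and some formula must be given. If the sentence is applied as written, a woman can leave or never enter the category while still breastfeeding.

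At stake is what Aim 3 estimates. Hypothesis 3 concerns how long women breastfeed. The literal definition would instead track time in one mixed-feeding pattern. Tx1 adds breastfeeding education and support, which may change the feeding pattern as well as its duration, so the coding need not affect the arms equally. The plan also intends to use the pilot results for sample-size estimation in a later study, so miscoded rates would carry forward.

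**Working it through.** The plan contains no figure that depends on this definition: the sample size is stated not to be based on power. The main check is therefore of the text.

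**Step 1. Status of each type of woman at 6 months**

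| Feeding at 6 months | Meets the 'any' definition? | Covered by the censoring sentence? | Has an event, going by the event wording? |
|---|---|---|---|
| Breast milk only | No, no formula | No | No, has not stopped |
| Mostly breast milk, some formula | Yes | Yes | No |
| Mostly formula, some breast milk | No, not predominant | No | No, has not stopped |
| No breast milk | No | No | Yes |

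Rows 1 and 3 are the problem. These women are neither events under one sentence nor censored under the other. An analyst must choose, and the only written definition of 'any' points away from counting them as continuing.

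**Step 2. Change over time.** Take a woman who feeds only breast milk to 3 months and then adds a little formula. Literally she is outside 'any' at week 1 and inside it at month 6. A category that can be entered late has no usable stopping time for a Cox model.

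**Step 3. Illustration of size.** Assumptions: the Section I.B rates of 29% (Kansas, high BMI) and 51% (Kansas, normal BMI) stand in for the true any-breast-milk rates *p* in a comparator arm and in Tx1. The plan does not predict these rates for the arms. Let *e* be the share of these women feeding exclusively and *m* the share giving mostly formula. Both are assumed, as the documents give neither. Everyone failing the definition is coded as stopped.

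- Literal rate = *p* × (1 − *e* − *m*)
- Relative risk (RR) of stopping = (1 − Tx1 rate) / (1 − comparator rate)

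| Assumed mix | Comparator | Tx1 | RR of stopping | Women continuing of 20 (comparator, Tx1) |
|---|---|---|---|---|
| Inclusive definition | 29.0% | 51.0% | 0.490/0.710 = 0.69 | 5.8, 10.2 |
| *m* = 20% in both; exclusive feeders kept in | 0.29 × 0.8 = 23.2% | 0.51 × 0.8 = 40.8% | 0.592/0.768 = 0.77 | 4.6, 8.2 |
| *e* = 20%, *m* = 20% in both | 0.29 × 0.6 = 17.4% | 0.51 × 0.6 = 30.6% | 0.694/0.826 = 0.84 | 3.5, 6.1 |
| *e* = 40%, *m* = 20% in both | 0.29 × 0.4 = 11.6% | 0.51 × 0.4 = 20.4% | 0.796/0.884 = 0.90 | 2.3, 4.1 |
| *e* = 20% comparator, 50% Tx1; *m* = 20% in both | 0.29 × 0.6 = 17.4% | 0.51 × 0.3 = 15.3% | 0.847/0.826 = 1.03 | 3.5, 3.1 |

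With equal mixes the relative risk moves toward 1. It passes 1 only in the last row, where Tx1 is assumed to shift strongly to exclusive feeding.

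**The case against.** The best defence is that the authors almost certainly meant the inclusive sense. The event is worded as stopping breastfeeding, exclusivity is introduced as an additional measure, and Table 5 pairs 'any' with 'exclusive'. A sensible analyst would not record a stop for a woman who is fully breastfeeding. Formula and solids are to be recorded by first introduction, quantity and frequency, so much of the classification could be recovered. The trial is also a pilot not powered for efficacy.

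Most of this stands as a reading of intent. It does not supply the missing rule: the one operational definition says otherwise, and the censoring sentence relies on the defined term.

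A reader might infer more than the documents support:

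- *That the plan flatly counts these women as stopped.* It does not; its event wording conflicts with its definition.
- *That Section I.B gives a clean inclusive definition shared by all its benchmarks.* It attaches the term only to the 29%, not to the 61% goal, and its own wording also leaves out exclusive feeders.
- *That misclassification is concentrated among Hispanic women.* Section I.F says they often supplement with formula, not that formula predominates. Breast milk with some supplementation is what the definition includes.
- *That the initiation definition, "This is defined as starting breastfeeding immediately after delivery", adds to the problem.* It is narrow, but initiation is not a listed primary outcome and no model is specified for it.

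**Conclusion.** The point holds as a defect in a stated rule. The only operational definition of any breastfeeding omits two groups of women who are still breastfeeding, and the Aim 3 analysis uses that term for censoring while wording the event differently. Two analysts following the same plan could code the same women differently on a primary outcome.

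That conclusion rests on the text alone. The size and direction of any bias cannot be determined from the documents. The range of 0.77 to 1.03 against 0.69 depends on borrowed background rates, assumed feeding mixes and the least favourable coding. The apparent reversal needs an assumed 50% versus 20% split in exclusive feeding, so it shows what is possible and is not a forecast.

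**What to change.** 1. **Section III, Outcome Measures, Aim 3.** Define any breastfeeding as receipt of any breast milk, whether alone or with formula or solids. Make exclusive breastfeeding a nested subset. Keep predominant feeding as a secondary category, with a stated threshold.
2. **Section III, Statistical Analysis, Aim 3.** Define the event as complete cessation of breast milk. For the Cox model, set the event time at the last breast-milk feed and administratively censor women still giving any breast milk at 6 months. For the modified Poisson model, define the outcome as no breast milk being given at the 6-month visit. State how 'being given' is judged at that visit, identically in all arms and consistently with the last-feed date, so that the two models cannot disagree about the same woman.
3. **Section I.B.** Align the wording of the term. If the source of the 29% used a different definition, say so and do not compare the trial's rate with it directly.

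The cost is wording plus one data-entry item (whether any breast milk is still given and, if not, the date of the last feed) at visits already in Table 5. No visits are added.
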